##### **Hepatitis C Virus testing**

Patients with hepatitis C risk factors and additional patients at the discretion of the investigator should be tested for HCV RNA-PCR test at baseline. For a list of hepatitis C risk factors, refer to Section 3.2.5.

**Note – serologic testing is not mandatory for all subjects. Rather, each subject needs to be screened by history taking for risk factors and ONLY if they are at risk for HBV or HCV should serologic testing be performed.**

#### 4.7 Data and Safety Monitoring

Subject accrual and all reported serious adverse events will be monitored at the University of Chicago during the weekly Phase 2 Conference. This meeting will include study investigators, independent investigators, and study coordinators. Quarterly reports of completed and missing Case Report Forms will be generated and reviewed by the principal investigators.

A Data and Safety Monitoring Board (DSMB) will be convened to review toxicity and efficacy data. The DSMB will consist of a statistician and two experts in SCCHN. DSMB members cannot be investigators or co-investigators involved in the clinical trial. After the annual meeting of the DSMB a report to the principal investigators will be issued recommending study continuation/discontinuation or proposed changes to the protocol.

Toxicity will be reviewed annually, with the first review approximately coinciding with the first 30 patients being enrolled and on-treatment for at least 3 months. A single formal interim analysis will take place after 36 events have occurred, which corresponds to 50% of the expected number of on-study events. The DSMB may be convened more often should significant toxicities be observed. The guideline to stop early for futility will be if the conditional power at the interim look is less than 10% using the stochastic curtailment approach (as described in Jennison and Turnbull). Based on this approach, the effect of adding the interim look on overall power will be negligible (Jennison C, Turnbull BW. Group Sequential Methods: Applications to Clinical Trials. 1999. Chapman & Hall/ CRC).

## 5 Data management

### 5.1 Data collection

Investigators must record the information required by the protocol. Case Report Forms (CRF) will be made available for all data elements required by the study. CRFs should be faxed or emailed to the Study Coordinator at [contact].

## 6 Statistical methods

### 6.1 Statistical methods

This is a multicenter, randomized, placebo-controlled, double-blind Phase II clinical trial of adjuvant Everolimus vs. placebo. Patients will be randomized 8-16 weeks after the completion of curative intent therapy. The primary endpoint is 2-year progression-free survival (PFS) rate. Progression-free survival will be estimated using the method of Kaplan-Meier, and compared between the two treatment arms using the stratified logrank test. Multivariate regression models will be used to compare treatment effect between treatment groups adjusting for other important prognostic factors. Adverse event rates will be summarized and compared between treatment groups using Chi-squared or Fisher's exact test. Continuous variables will be compared between groups using t-test or Wilcoxon rank sum test as appropriate, and categorical variables will be compared using Cox Regression Analysis. Regression models will be used as part of exploratory analysis to explore treatment effects adjusting for other important prognostic factors. The guideline to stop early for futility will be if the conditional power at the interim look (Section 4.7) is less than 10% using the stochastic curtailment approach (as described in Jennison and Turnbull).

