### Secondary

- Toxicity of everolimus versus placebo as adjuvant therapy
- Site of disease progression (locoregional vs. distant) in subjects treated with everolimus versus placebo
- Incidence of second primary tumors in subjects treated with everolimus versus placebo
- Prevalence of Akt/mTOR pathway activation in locally advanced SCCHN
- Determine correlation between progression free survival (PFS) and the degree of activation of the Akt/mTOR pathway biomarkers in tumors and adjacent mucosa treated with everolimus versus placebo
- Determine if PTEN status is predictive marker of Everolimus sensitivity

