### **3.2.4 Monitoring of Everolimus suspected toxicities**

Patients whose treatment is interrupted or permanently discontinued due to an adverse event or abnormal laboratory value suspected to be related to Everolimus must be followed at least weekly until the adverse event or abnormal laboratory resolves or returns to grade 1. If a patient requires a dose delay of > 21 days from the intended day of the next scheduled dose, then the patient must be discontinued from the study.

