### **3.2.5 Known Undesirable Side Effects of Everolimus**

The data described below reflect exposure to everolimus (n=274) and placebo (n=137) in a randomized phase III study for the treatment of metastatic renal cell carcinoma. In total, 165 patients were exposed to everolimus 10 mg/day for  $\geq$ 4 months. The median age of patients was 61 years (range 27 to 85). The most common adverse reactions (incidence  $\geq$ 10%) were stomatitis, rash, fatigue, asthenia, diarrhea, anorexia, nausea, mucosal inflammation, vomiting, cough, peripheral edema, infections, dry skin, epistaxis, pruritus, and dyspnoea. The most common grade 3-4 adverse reactions (incidence  $\geq$ 2%) were infections, stomatitis, fatigue, and pneumonitis.

The median duration of blinded study treatment was 141 days (range 19 to 451) for patients receiving everolimus and 60 days (range 21 to 295) for those receiving placebo. The rates of treatment-emergent adverse reactions resulting in permanent discontinuation were 7% and 0% for the everolimus and placebo treatment groups, respectively. Most treatment-emergent adverse reactions were grade 1 or 2 in severity. Grade 3 or 4 treatment-emergent adverse reactions were reported in 39% versus 7% of patients receiving everolimus and placebo, respectively. Deaths due to acute respiratory failure (0.7%), infection (0.7%), and acute renal failure (0.4%) were observed on the everolimus arm.

Everolimus has immunosuppressive properties and may predispose patients to bacterial, fungal, viral or protozoan infections, including infections with opportunistic pathogens. Localized and systemic infections, including pneumonia, other bacterial infections, invasive fungal infections, such as aspergillosis or candidiasis and viral infections including reactivation of hepatitis B virus, have been described in patients taking everolimus. Some of these infections have been severe (e.g. leading to respiratory or hepatic failure) and occasionally have had a fatal outcome.

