### **3.4.4 Safety assessments**

Safety assessments will consist of monitoring and recording all adverse events and serious adverse events, the regular monitoring of hematology, blood chemistry and urine values, regular measurement of vital signs and the performance of physical examinations.

These assessments should be performed within  $\pm 2$  days of the scheduled day of assessment except for adverse events that will be evaluated continuously through the study. Safety and tolerability will be assessed according to the NIH/NCI CTC [http://evs.nci.nih.gov/ftp1/CTCAE/CTCAE\\_4.03\\_2010-06-14\\_QuickReference\\_5x7.pdf](http://evs.nci.nih.gov/ftp1/CTCAE/CTCAE_4.03_2010-06-14_QuickReference_5x7.pdf).

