#### **3.4.4.1 Adverse events**

Information about all adverse events, whether volunteered by the subject, discovered by investigator questioning, or detected through physical examination, laboratory test or other means, will be collected and recorded and followed as appropriate.

An adverse event is the appearance or worsening of any undesirable sign, symptom, or medical condition occurring after starting the study drug even if the event is not considered to be related to study drug. Medical conditions/diseases present before starting study drug are only considered adverse events if they worsen after starting study drug. Abnormal laboratory values or test results constitute adverse events only if they induce clinical signs or symptoms, are considered clinically significant, or require therapy.

The occurrence of adverse events should be sought by non-directive questioning of the patient at each visit during the study. Adverse events also may be detected when they are volunteered by the patient during or between visits or through physical examination, laboratory test, or other assessments. As far as possible, each adverse event should be evaluated to determine:

1. the severity grade (mild, moderate, severe) or (grade 1-4)
2. its relationship to the study drug(s) (suspected/not suspected)
3. its duration (start and end dates or if continuing at final exam)

4. action taken (no action taken; study drug dosage adjusted/temporarily interrupted; study drug permanently discontinued due to this adverse event; concomitant medication taken; non-drug therapy given; hospitalization/prolonged hospitalization)
5. whether it constitutes a serious adverse event (SAE)

Grading for all adverse events will utilize NCI CTCAE v4.0.

CTCAE version 4.0 is available at: <http://ctep.cancer.gov/reporting/ctc.html>

All adverse events should be treated appropriately. Such treatment may include changes in study drug treatment including possible interruption or discontinuation, starting or stopping concomitant treatments, changes in the frequency or nature of assessments, hospitalization, or any other medically required intervention. Once an adverse event is detected, it should be followed until its resolution, and assessment should be made at each visit (or more frequently, if necessary) of any changes in severity, the suspected relationship to the study drug, the interventions required to treat it, and the outcome.

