#### 4.6 Reporting of Adverse Events

Serious Adverse Events that require phone reporting within 24 hrs per section 3.4.4.2 should be phoned and emailed to the University Of Chicago Cancer Clinical Trials Office (CCTO) at [contact] and faxed to Novartis Clinical Safety and Epidemiology Department. [contact]) by the end of the business day during which the investigator becomes aware of the event or by 12 noon the following day if the event occurs after normal business hours.

The following information is required when calling in the event:

- Reporter's Name and Telephone Number

- Patient Initials
- Patient Medical Record Number
- IRB Protocol Number
- PI of Study
- Attending Physician
- Date of Event
- Description of Event (including grade of the event and if the event required hospitalization)

Upon receipt of the 24-hour notification, the CCTO will send an e-mail to the research nurse, attending physician, all PI's, and to Novartis Pharmaceuticals CS&E Department [contact]).

All serious adverse events, except those exempted from reporting per section 3.4.4.2, must be reported to the University of Chicago Cancer Center Clinical Trials Office in writing within **10 calendar days of event occurrence (5 calendar days for an unexpected grade 4 or 5 event, or death within 30 days of discontinuing investigational therapy)**. MedWatch form (FDA form 3500A) should be utilized. Report should also be submitted to the affiliate institution's local IRB according to institutional guidelines. Reports should be sent to the address or fax number below with any appropriate source documentation.

Quality Assurance Coordinator  
Cancer Clinical Trials Office  
University of Chicago, MC 1140  
[name]  
[name]  
[contact]  
Email: [[contact]](mailto:[contact])

Adverse Events will be recorded and followed until the adverse event has subsided and abnormal findings have returned to normal or stabilized. In addition, any events with a suspected causal relationship to Novartis study drug will be reported as AEs or SAEs (as applicable) throughout follow-up.

The sponsor will stop the study at any time if new knowledge is obtained indicating that:

- Safety for all participating patients can no longer be assumed; and/or
- The risk-benefit ratio is no longer acceptable for the participating patients.

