New adverse events for patients who discontinue the study will not be recorded past their date of discontinuation but events that are ongoing will be followed, if feasible, until they resolve. All patients will be followed for survival.

A weekly report of delinquent or pending documents will be forwarded to [name] (U of C Events Only). All delinquent reporting (greater than 10 days from event occurrence) must include documentation of reason for delinquency and may require implementation of an action plan.

SAEs that have not resolved at the time of reporting should have a follow up written report within 10 calendar days of resolution. This includes any pregnancies in which the outcome, including spontaneous or voluntary termination, details of birth, and the presence or absence of any birth defects, congenital abnormalities or maternal and newborn complications should be reported.

Once the appropriate SAE documents have been received, the University of Chicago Cancer Center Clinical Trials office forwards these to the Principal Investigator. The Principal Investigator should comment on the outcomes of the event or problem including likely relationship to study drug. The Principal Investigator should also indicate whether he/she concurs with the details of the report provided by the study investigator and provide any recommendations for actions to be taken in response to the SAE.

Once the University of Chicago Cancer Center Clinical Trials Office receives the Principal Investigator's report, they will forward all documents to the IRB, research nurse, all participating institutional PI's, the FDA, and Novartis [contact]).

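### The adverse event comparison in Section 6.1 takes no account of unequal, partly off-drug recording time, so it can be biased in either direction

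*Combined protocol and SAP*

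**What the plan says.** - **Objective.** Section 2 lists "Toxicity of everolimus versus placebo as adjuvant therapy" first among the secondary objectives.
- **Analysis.** Section 6.1: "Adverse event rates will be summarized and compared between treatment groups using Chi-squared or Fisher's exact test". No window, exposure adjustment or time-to-event method is given for adverse events.
- **Collection in the study.** Section 3.4.4 sets a visit tolerance "except for adverse events that will be evaluated continuously through the study". Section 3.4.4.1 adds "The occurrence of adverse events should be sought by non-directive questioning of the patient at each visit during the study". Neither ties the end of collection to the last dose.
- **Treatment and follow-up.** Drug is given for at most 1 year (3.3.1). Follow-up is at least 2 years (3.1). Table 3-4 runs to week 144, but only patients enrolled early get that far.
- **Collection after leaving.** Section 4.6: "New adverse events for patients who discontinue the study will not be recorded past their date of discontinuation". The same section also says "any events with a suspected causal relationship to Novartis study drug will be reported as AEs or SAEs (as applicable) throughout follow-up".
- **Routes out of the study.** For a dose delay of more than 21 days, Section 3.2.4 says "then the patient must be discontinued from the study". Table 3-5 withdraws patients whose grade 2 or 3 pneumonitis has not recovered within 3 weeks. The list after that table includes disease progression as a reason for leaving. Section 3.3.3 requires withdrawal before other anticancer therapy is given.

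**The concern.** Chi-squared and Fisher tests on the share of patients with an event compare like with like only if the arms are observed for similar time under similar conditions. Three features here work against that:

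1. In a patient who completes treatment, about half or more of the recorded time is off drug. Background events in that period pull the two arms together.
2. A patient who leaves because of toxicity cannot contribute later events of other kinds. If such exits are commoner on everolimus, the everolimus proportion falls.
3. A patient who leaves because of progression is also cut short. If everolimus delays progression as planned, placebo patients leave earlier and the placebo proportion falls.

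The second and third pull in opposite directions. At stake is whether the trial's toxicity comparison, which matters a great deal for a drug given to patients with no evidence of disease, can be read at face value.

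**Working it through.** **Design inputs (Section 6.1, Sample Size).** The plan states no power or rate for adverse events, so there is no figure on this point to reproduce. Its PFS figures do reproduce: HR = ln(0.5)/ln(0.7) = 1.943 (stated 1.94), and Freedman's formula needs 77 events, which at a mean event probability of 0.5735 gives N of about 134 (stated 132). The monthly progression hazards are ln(2)/24 = 0.02888 on placebo and −ln(0.7)/24 = 0.01486 on everolimus.

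**Direction: closed form over 12 months.** Assume constant hazards and treat every progression as study exit. With adverse event hazard *a* and exit hazard *e*, the crude proportion is a/(a+e) × [1 − exp(−12(a+e))]. Give both arms the same true 30% risk, so a = −ln(0.7)/12 = 0.02972.

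| Arm and 12-month toxicity exit | e | Crude proportion |
|---|---|---|
| Placebo, none | 0.02888 | 25.6% |
| Everolimus, none | 0.01486 | 27.6% |
| Everolimus, 40% | 0.05743 | 22.1% |

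With no true difference, the crude comparison shows an excess on everolimus in one case and a deficit in the other. The sign changes where the toxicity exit hazard equals 0.02888 − 0.01486 = 0.01402, that is at 1 − exp(−12 × 0.01402) = 15.5% exit by 12 months.

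**Off-drug dilution alone.** Borrow 39% and 7% (grade 3–4 reactions in the renal cancer trial, Section 3.2.5) as 12-month risks, with no exits. Add 12 off-drug months at the placebo rate in both arms:
- everolimus: 1 − 0.61 × 0.93 = 43.3%
- placebo: 1 − 0.93² = 13.5%
- the risk ratio falls from 39/7 = 5.57 to 43.3/13.5 = 3.20, and the difference from 32.0 to 29.8 points.

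**Exposure in the plan's own cited data.** In that renal cancer trial, median treatment was 141 versus 60 days. The crude ratio of 5.6 becomes (39/141)/(7/60) = 2.4 per unit of median exposure. This is rough, but there the crude ratio is the larger one.

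**Size: simulation.** Assumptions: 80 per arm; background 3% per month; the ratio applies only on drug, up to 12 months; follow-up 24–36 months; every progression is study exit; the event studied is not the one that causes exit. The plan's method is any event before study exit, tested by Fisher, two-sided 0.05. The alternative is on-drug first events per person-month, tested by an exact conditional binomial test.

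| True ratio | 2-year PFS, everolimus/placebo | Toxicity exit, everolimus/placebo | Fisher significant | Person-time significant |
|---|---|---|---|---|
| 2 | 70/50 | 7% / 0% | 55% | 73% |
| 2 | 70/50 | 25% / 3% | 27% | 66% |
| 2 | 50/50 | 25% / 3% | 10% | 69% |
| 1 | 70/50 | 10% / 3% | 6.7%, nearly all against everolimus | 3–5% |
| 1 | 50/50 | 40% / 3% | 24%, nearly all favouring everolimus | 3–5% |

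In the fourth row the crude proportions are about 46% versus 41%; in the fifth, 31% versus 41%. Repeat runs moved the power figures by up to about 3 points.

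**A large excess.** With 39% versus 7% as true 12-month risks, Fisher power as written is about 99%, 94% and 87% at 7%, 25% and 40% toxicity exit (PFS 70/50), and 78% at 40% exit with no PFS benefit.

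**The case against.** A reader might infer that the plan understates everolimus toxicity. The documents do not support a fixed direction. Under the protocol's own PFS assumption, placebo patients leave earlier for progression, and the crude test then tends to overstate everolimus toxicity until toxicity exit is substantial. Exit rates of 25% or 40% have no source in the documents. The only related figure is 7% versus 0% discontinuation for adverse reactions in the renal cancer trial. Treatment there was shorter, so 7% is not a ceiling, but it is far from 40%.

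Other points also limit the concern. The event that causes exit is already counted, and ongoing events are followed. Section 4.6 keeps suspected drug-related events reportable throughout follow-up. Table 3-1 mostly stops drug rather than participation, and a patient who stops drug but stays remains under collection. Fisher tests on proportions are a conventional phase 2 safety summary, and the DSMB reviews toxicity separately.

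All of this stands as a limit on direction and size. It does not remove the flaw. The exception in 4.6 depends on the investigator's suspicion, whereas the adverse event definition in 3.4.4.1 includes events judged unrelated. Patients who stop drug and stay add off-drug time. A bias of unknown sign is still a reason to define the window.

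**Conclusion.** The flaw is real: the only stated toxicity comparison ignores recording time that is unequal and partly off drug. The bias can go either way. Off-drug time pulls toward no difference, toxicity exits on everolimus hide later events, and earlier progression exits on placebo can produce a false everolimus excess. For a common event with a true on-drug ratio of 2, the loss ranges from moderate (55% versus 73% power) to severe (10% versus 69%). The severe end needs both a high assumed exit rate and no PFS benefit. A marked excess would usually still be detected. These figures rest on constant hazards, exit independent of the event studied, every progression counted as exit, and assumed rates. This should be corrected, but it does not touch the primary endpoint.

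**What to change.** In Section 6.1, replace the adverse event sentence with wording such as:

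*Adverse events will be compared over a common window from first dose to 30 days after last dose. The main comparison will be [time to first event / exposure-adjusted incidence with a rate ratio and 95% CI]. Time at risk ends at the first event, the end of the window or the end of recording, whichever comes first. Crude proportions will be shown beside it. Events after the window will be tabulated separately.*

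The two measures are related but not identical, so one must be named as the main comparison. The 30 days match the serious adverse event period in 3.4.4.2. Neither measure makes exit for toxicity uninformative, so numbers and reasons for leaving should be shown by arm.

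Two sets of passages must also be reconciled, because they decide whose events are recorded:
- within Section 4.6, reporting of suspected drug-related events throughout follow-up, and no recording of new events after discontinuation;
- Table 3-1, which discontinues everolimus, and Section 3.2.4 with Table 3-5, which discontinue or withdraw the patient from the study.

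Cost: SAP wording and a little programming. Event start dates (3.4.4.1), dose records (3.3.1) and diaries (3.3.4) are already collected. The rate version assumes a roughly constant rate; time to first event avoids that.

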### 3.4.2 Visit schedule

**Table 3-4 Evaluation and visit schedule**

Examination	Screening/ Baseline	Week									
		4	16	32	52	64	80	96	112	128	144
Informed consent	X										
No Evidence of Disease	X										
Inclusion/exclusion criteria	X										
Tissue Biopsy	X										
Radiographic assessment	X										
Physical examination	X										
ECG	X										
Laboratory test	X	X	X	X	X	X	X	X	X	X	X
Research Blood Draw	X	X	X		X						
HBV-DNA, HbsAg, HBs Ab, HBs Ab, HCV-RNA-PCR^6	X										
Patient Questionnaire	X										
Follow Up Form^8		X	X	X	X	X	X	X	X	X	X

See Section 3.2.2

See Section 3.4.7; Tissue biopsy must have been obtained PRIOR to curative intent therapy

Baseline radiographic assessment (CT, PET-CT, PET and/or MRI as appropriate) must be preformed within 12 weeks of starting everolimus. CT, PET-CT, PET and/or MRI as appropriate should be performed at least every 4-6 months in years 1 and 2 then every 6 months in year 3.

Baseline assessments must be performed within 7 days of starting everolimus. Hemoglobin, platelets, total white blood cell count (WBC), and differential; sodium, potassium, chloride, bicarbonate, calcium, glucose, creatinine, blood urea nitrogen, albumin, total protein, SGOT (AST), SGPT (ALT), total bilirubin, alkaline phosphatase, uric acid, phosphorus, serum lipid profile (triglycerides, total cholesterol, HDL and LDL); PT (INR) evaluation only at baseline unless otherwise indicated. Patients should be fasting at the time of the blood sampling.

Blood draw for serum, whole blood and optional PBMC isolation (see Section 3.4.7). Serum will be drawn at screening, weeks 4, 16 and 52. Whole blood will be drawn at weeks 4, 16 and 52. Optional PBMC will be drawn at screening and week 4.

All patients should be **screened** for hepatitis risk factors and any past illnesses of hepatitis B and hepatitis C infection. If the patient has any of the risk factors outlined in section 3.4.1 then serologic testing must be done.

All patients should fill out the Patient Questionnaire prior to first dose. See the Study Procedures manual.

See the Study Procedures Manual

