**Peripheral Blood Mononuclear Cells (PBMC) (optional procedure based on the sites ability to process sample):**

Venous blood sample will be collected prior to therapy and at week 4 in 1 blue and black tiger top tube (~8 cc). See Appendix D for PBMC isolation protocol. Sample should be labeled with institution, protocol number, patient initials, patient registration number, and the date and time of draw. PBMC sample should be stored at -80°C till shipment. PBMC sample should be shipped with accompanying Sample Shipping Form and Notification of Correlative Study Samples Shipment form (Appendix C) to LSUHSC in Shreveport for correlative studies at the address indicated below. (As this is an adjuvant trial, patients will not have any post-treatment tumor tissue. Hence, biomarker changes in PBMC can be used as surrogate marker of tumor response.)

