**Serum and whole blood:**

Serum samples will be collected prior to therapy on all patients and at weeks 4, 16 and 52 in three 7-10 cc gold top tubes. Blood in the serum collection tube should be allowed to clot for 60 minutes and then centrifuged to separate serum. Serum should be stored in 2 mL cryovial tubes (Nalgene Cat# 5000-0020) in 410uL aliquots. Samples should be labeled with institution, protocol number, patient initials, patient registration number, and the date and time of draw. Serum samples should be stored at -80°C till shipment. Serum samples collected from two gold top tubes should be shipped with a copy of accompanying Sample Shipping Form and Notification of Correlative Study Samples Shipment form (Appendix C) to LSUHSC in Shreveport for correlative studies at the address indicated below. Serum samples collected from one gold top tube should be shipped with accompanying Sample Shipping Form (Appendix C) to the University of Chicago at the address indicated below.

Whole blood samples will be collected on all patients at weeks 4, 16 and 52 in 1 lavender top tube (10 cc). The tube will be inverted several times to mix contents of the tube immediately after collection of the blood sample. Samples should be labeled with institution, protocol number, patient initials, patient registration number, and the date and time of draw. Freeze at

-80°C within 60 minutes of draw until shipment. Whole blood samples collected from one lavender top tube should be shipped with accompanying Sample Shipping Form (Appendix C) to the University of Chicago at the address indicated below.

We may store all samples until publication of the study results to potentially address reviewers concerns. It is not expected that any study samples will remain at the conclusion of the study as we have proposed an extensive number of biomarkers to analyze.

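### Section 6.1 leaves continuous outcomes undefined and names only unadjusted tests for them, so comparisons of on-treatment laboratory, serum or PBMC measures would not adjust for the pre-therapy value already collected

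*Combined protocol and SAP*

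**What the plan says.** The combined protocol and SAP has one sentence in section 6.1 on testing continuous data: "Continuous variables will be compared between groups using t-test or Wilcoxon rank sum test as appropriate". It names no variable, no visit, no form of the outcome and no covariate. Section 6.1 also provides for adjusted models, one of them worded as "Regression models will be used as part of exploratory analysis to explore treatment effects adjusting for other important prognostic factors". The pre-therapy value of the outcome being analysed is not mentioned there.

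The pre-therapy values themselves are scheduled:

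- **Laboratory tests** (Table 3-4, footnote 4): "Baseline assessments must be performed within 7 days of starting everolimus". They are repeated at every later visit, with PT (INR) normally at baseline only.
- **Serum** (Table 3-4, footnote 5): "Serum will be drawn at screening, weeks 4, 16 and 52". Section 3.4.7 says the same: "Serum samples will be collected prior to therapy on all patients and at weeks 4, 16 and 52".
- **PBMC** (Table 3-4, footnote 5): "Optional PBMC will be drawn at screening and week 4". Section 3.4.7 agrees: "Venous blood sample will be collected prior to therapy and at week 4". The sample is optional and depends on the site's ability to process it.
- **Whole blood** (Table 3-4, footnote 5) has no pre-therapy draw: "Whole blood will be drawn at weeks 4, 16 and 52".

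**The concern.** A two-sample t-test or rank-sum test on a follow-up measurement ignores what the same patient's earlier measurement says about it. When the two are correlated, part of the spread between patients was present before treatment and can be removed by including the earlier value in the model. Without it the arm difference is estimated less precisely, and any chance baseline imbalance between arms carries into a comparison of final values.

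What is at stake is the supporting evidence. Section 1.1.3.3 lists reduced blood counts, hyperlipidemia and hyperglycemia among the more frequent laboratory findings with everolimus. Section 3.4.4.1 counts an abnormal laboratory value as an adverse event only if it causes signs or symptoms, is considered clinically significant or needs therapy. Smaller shifts would therefore show only in a continuous comparison. Section 3.4.7 notes that no post-treatment tumor tissue will exist and proposes change in PBMC markers as a surrogate of tumor response. Because PBMC sampling is optional, that set may be the smallest, and precision is worth most there.

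The lack of definition is a second gap. With variables, visits and form all open, the choice between final value and change could be made after the data are seen.

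**Working it through.** **Inputs.** The documents give no sample size, SD, effect size or correlation for any continuous outcome, so there is no plan figure on this point to reproduce. The only sample size calculation is for PFS (section 6.1, Sample Size: 66 per arm before the allowance for loss, 80 per arm enrolled). Its hazard ratio reproduces as ln(0.5)/ln(0.7) = 1.94. It does not depend on how continuous variables are analysed.

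Assumptions: r, the correlation between the pre-therapy and follow-up values, from 0.3 to 0.8; the same SD at both times; 1:1 allocation.

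**Variance of the arm difference**, relative to a t-test on final values (= 1):

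- t-test on change from baseline: 2(1 − r)
- linear model with arm and baseline value: 1 − r²

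The reduction from adjustment is therefore r² against final values. Against change scores it is 1 − (1 − r²)/[2(1 − r)] = (1 − r)/2.

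| r (assumed) | Change score | Adjusted | Reduction vs final value | Reduction vs change |
|---|---|---|---|---|
| 0.3 | 1.40 | 0.91 | 9% | 35% |
| 0.5 | 1.00 | 0.75 | 25% | 25% |
| 0.6 | 0.80 | 0.64 | 36% | 20% |
| 0.7 | 0.60 | 0.51 | 49% | 15% |
| 0.8 | 0.40 | 0.36 | 64% | 10% |

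**What this means for power.** As an illustration, take a true difference of 0.45 SD (assumed) and two-sided alpha 0.05, using the noncentral t and one degree of freedom for the covariate. The effect in SD units is divided by √(1 − r²) for the adjusted model and by √[2(1 − r)] for change.

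| Per arm | r | Final value | Change | Adjusted |
|---|---|---|---|---|
| 66 | 0.3 | 73% | 58% | 77% |
| 66 | 0.5 | 73% | 73% | 84% |
| 66 | 0.6 | 73% | 82% | 89% |
| 66 | 0.7 | 73% | 91% | 95% |
| 40 | 0.3 | 51% | 39% | 55% |
| 40 | 0.5 | 51% | 51% | 63% |
| 40 | 0.6 | 51% | 60% | 70% |
| 40 | 0.7 | 51% | 73% | 80% |

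The 40 per arm is an assumed size for an optional sample such as PBMC. At the enrolled 80 per arm, the unadjusted final-value test has 81% power for the same difference.

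**Detectable difference.** With 66 per arm and 80% power, the final-value test detects (1.960 + 0.842) × √(2/66) = 0.488 SD. Multiplying by √(1 − r²) gives 0.465 SD at r = 0.3, 0.422 at 0.5 and 0.348 at 0.7.

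The adjusted model does better than both unadjusted forms at every r shown. Which unadjusted form is better depends on r: change is worse than final value below r = 0.5 and better above it. An unspecified choice between the two therefore matters.

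**The case against.** The strongest reply is that section 6.1 does not say its sentence covers on-treatment measures at all. It refers to comparison between groups, which could mean baseline characteristics by arm. It could also mean the section 3.4.7 hypothesis that pathway expression is higher in patients who recurred than in those who did not. That comparison uses tissue taken before curative therapy and has no earlier value to adjust for. For PBMC, section 3.4.7 speaks of changes, so the pre-therapy value may already be used there. All of this stands, and it is why the point is conditional on where the sentence is applied. It does not remove the point: no other method is named for continuous variables, and the change-score reading alters the gain without eliminating it.

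A reader might infer that the plan gives up a quarter to a half of the information. The documents do not support that. It needs both an assumed r of about 0.5 to 0.7 and an analysis of final values, and the plan states neither. Against change scores the loss at those correlations is 25% to 15%.

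A reader might also infer that the toxicity objective rests on these tests. It does not. Toxicity is graded by CTCAE, and section 6.1 compares adverse event rates by chi-squared or Fisher's exact test. No objective in section 2 names a between-arm comparison of a continuous on-treatment measure.

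The exploratory regression sentence partly answers the concern, since a pre-therapy value could be counted as a prognostic factor. But it does not name that value, and it does not replace the method stated for continuous variables.

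**Conclusion.** The concern holds in limited form. Section 6.1 does not define its continuous outcomes, and the only method it names for them is unadjusted. If that method is used for between-arm comparisons of laboratory, serum or PBMC measures after baseline, it is less precise than the scheduled data allow. The shortfall in precision is 9% to 64% of the variance against final values, or 35% down to 10% against change scores, for r from 0.3 to 0.8. The range rests on an assumed r, equal SDs at the two times and a linear relation; the 0.45 SD difference and 40 per arm in the power table are also assumptions. At r = 0.3 the gain over final values is small (73% to 77% power at 66 per arm).

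This is a secondary and exploratory matter of precision and specification. The primary PFS comparison, its sample size, its error rates and the adverse event comparison do not change.

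**What to change.** In section 6.1, list the continuous outcomes and the visits at which they will be compared, and add wording such as:

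> Between-arm comparisons of post-baseline continuous measures that have a pre-therapy value (laboratory, serum and, where collected, PBMC) will use a linear model with treatment arm and the pre-therapy value of the same measure, on the log scale or in a rank-based version where the distribution is skewed. The t-test or Wilcoxon rank sum test will be used for baseline variables, for measures without a pre-therapy value (such as whole blood), and for comparisons of pre-treatment tissue.

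The last sentence is needed. If the unadjusted tests were restricted to baseline variables, whole-blood measures and the tissue comparison in section 3.4.7 would have no stated method.

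The cost is an edit to the analysis text. The pre-therapy values are already scheduled, so no samples, visits or patients are added.
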